9.7 Interim Analyses

During the in-life portion of the trial, descriptive summary level results (PK, PD and/or safety (labs, VS, ECGs) may be prepared as needed to support dose escalation meetings. No individual level results will be provided, and the aggregate summaries will be presented in a blinded manner. There are no planned interim analyses to test any formal hypotheses.

9.8 Multiplicity

Since there are no pre-specified primary hypotheses, no adjustments for multiplicity are needed.

9.9 Sample Size and Power Calculations

A sample size of six subjects on active dose and two on placebo per panel is considered to be adequate to address the primary objectives of the study.

Pharmacokinetics

The sample size selected for each dose level to evaluate the effect of ESRD on HD on the PK of MK-2060 compared to subjects with normal renal function was not chosen to satisfy any a priori statistical requirement. Nevertheless, estimates of the expected precision of the estimates, based on these sample sizes and the variability obtained from previous studies are presented below.

The precision of the estimated ratios of geometric means (ESRD on HD/normal renal function, at the same dose level) of PK parameters obtained from this study can be assessed by calculating the half-width of the 90% CIs expected for the given sample size and assumed variability. The between-subject standard deviations (on the natural log scale) for MK-2060 AUC0-168hr and Cmax after administration of 20mg IV MK-2060 observed in a previous

study (PN001) are $0.199 \ln(\mu\text{M}^*\text{hr})$ and $0.169 \ln(\text{nM})$, respectively. Since the between subject variability in subjects with RI has historically been seen to be 2 to 3-fold higher in many studies, the between subject variability obtained from normal renal function subjects was inflated by a factor of 2 for ESRD on HD and was used for the following calculations. With a sample size of 6 subjects per population (6 20mg IV ESRD on HD and 6 20mg IV historical normal renal function, at the same dose level) and observed between-subject SDs as given above, then the half width of the 90% CIs of GMRs for MK-2060 AUC0-168hr and Cmax on the log scale will be 0.329 and 0.279, respectively. The lower and upper 90% confidence limits for the true GMRs will be given by $\text{OBS}/1.39$ and $\text{OBS}^*1.39$ for AUC0-168hr and $\text{OBS}/1.32$ and $\text{OBS}^*1.32$ for Cmax, respectively, where OBS is the observed GMR. Thus, for example, if the observed GMR for AUC0-168hr was 1.50 after administration of 20mg IV MK-2060, then the 90% CI for the GMR would be 1.08 to 2.08.

Pharmacodynamics

Part 1:

If the true CV is 30%, there is approximately 72.3% probability of yielding at least 60% posterior probability that the true fold increase is at least 1.5 if the true fold increase in aPTT after 168 hours of a single well-tolerated subcutaneous dose relative to placebo is at least 1.5. The total participants per dose is 8 (active = 6, placebo = 2).

Part 2:

If the true CV is 30%, for a total of approximately 20 participants (active = 15, placebo = 5), there is approximately 84% probability of yielding at least 60% posterior probability that the true fold increase is at least 1.5. We assume that the true fold increase in aPTT after 168 hours of a single well-tolerated subcutaneous dose relative to placebo is at least 1.5.

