
Part 1:
 
• Objective: To compare the plasma pharmacokinetics of MK-2060 following a single dose IV administration in older adult participants with ESRD on HD to participants with normal renal function (historical controls in PN001).• Estimation: In older adult participants with ESRD on HD, PK parameters (e.g. AUC_{0-∞}, Cmax) of MK-2060 following administration of a single dose will be estimated and compared to participants with normal renal function (historical controls in PN001).	
• Part 1: MK-2060 plasma AUC_{0-∞}, AUC₀₋₁₆₈, Cmax, C₁₆₈, T_{max}, terminal t_{1/2}, CL and V_z

Objectives	Endpoints
Tertiary/Exploratory	

Objective: Part 1: To explore the effect of MK-2060 given as a single IV dose on Factor XI (FXI) activity levels. Part 2: To explore the effect of MK-2060 given as multiple IV doses on Factor XI (FXI) activity levels.	a. FXI activity level fold change from baseline

Objective: Part 1: To explore the effect of MK-2060 given as a single IV dose on fibrin generation. Part 2: To explore the effect of MK-2060 given as multiple IV doses on fibrin generation.	b. Fibrin Generation Assay (FGA)

Objective: Part 1: To explore the effect of MK-2060 given as a single IV dose on prothrombin time (PT). Part 2: To explore the effect of MK-2060 given as multiple IV doses on prothrombin time (PT).	c. PT fold change from baseline

Objective: Part 1: To explore the effect of MK-2060 given as a single IV dose on biomarker(s) of inflammation (e.g., hsCRP). Part 2: To explore the effect of MK-2060 given as multiple IV doses on biomarker(s) of inflammation (e.g., hsCRP).	d. hsCRP reduction from baseline

Objectives	Endpoints

Objective: Part 1: To explore the effect of MK-2060 given as a single IV dose on time to hemostasis after decannulation of the hemodialysis vascular access site in ESRD patients. Part 2: To explore the effect of MK-2060 given as multiple IV doses on time to hemostasis after decannulation of the hemodialysis vascular access site in ESRD patients.	e. Time to adequate hemostasis after decannulation of vascular access compared to baseline

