4.2 Scientific Rationale for Study Design

The main objectives of this study are to evaluate safety, tolerability, PK, and PD of MK-2060 after IV administration of single and multiple doses in older adult (ages ≥ 40 and ≤ 80 for Part 1 and ≥ 18 and ≤ 80 for Part 2) men and women of non-child bearing potential (WONCBP) with ESRD on HD. PD effects on aPTT, PT, FXI activity, and fibrin generation will be explored. Up to approximately 44 older adult participants with ESRD on HD who meet study eligibility criteria may be enrolled in this study.

MK-2060 is being developed for the prevention of thrombotic complications in ESRD patients, thus the primary aim of this study is to evaluate safety, tolerability, PK, and PD of MK-2060 in this patient population.

We do not anticipate renal impairment, HD, or age to significantly alter the PK and PD of MK-2060. As discussed above, PN001 has demonstrated MK-2060 to be generally safe and well-tolerated in normal healthy subjects. Based on preliminary analysis, MK-2060 achieved mean maximum concentration at 1hr (end of infusion) after IV infusion, followed by a bi-phasic terminal phase with apparent mean half-life of ~29 to 39 days. MK-2060 clearance was ~0.23 L/day, consistent with reported CL of mAb. As renal elimination is typically an insignificant pathway for IgG mAbs due to their large size, the clearance of MK-2060 is not expected to change in renal impaired subjects or subjects on hemodialysis. Furthermore, assessment of the clotting cascade in subjects with ESRD has demonstrated that FXI levels are not significantly altered [Vaziri, N. D., et al 1994]. In PN001, MK-2060 volume of distribution was estimated as 11 L, slightly larger than the reported volume of distribution for mAb. [Dirks, N. L. 2010]. It could be possible that kidney failure or HD might impact volume of distribution, due to fluid retention, although we do not anticipate this to have a major effect. As MK-2060 is a monoclonal antibody age is also unlikely to alter PK and PD. The impact of renal impairment, HD, and age on MK-2060 PK and PD will be further

assessed by comparing data in this study to the data in young normal healthy subjects in PN001. IONIS has demonstrated using an FXI anti-sense oligo (ASO) that inhibition of the FXI pathway in ESRD patients on HD (mean age of 61 years) is generally safe and well-tolerated [Bethune, C., et al 2017]. Thus, the study of MK-2060 in older adult patients with ESRD on HD is well supported.

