9.6 Statistical Methods

Safety

Summary statistics and plots will be generated for raw laboratory safety tests, ECGs, and/or VS as well as for change from baseline, as deemed clinically appropriate. Depending on the safety parameter, the difference from baseline will either be computed on the original scale (raw change from baseline) or on the log scale and back-transformed for reporting (percent change from baseline).

Pharmacokinetics

Model-Based PK Summary

Part 1:

SD PK of participants with ESRD from the present study will be compared with historical SD PK data (P001) in healthy participants.

Separately for each PK parameter, individual values of AUC_{0-∞}, AUC_{0-168hr}, C_{max}, and C_{168hr} will be natural log-transformed and evaluated with a linear fixed effects model containing a categorical effect for population (ESRD on HD, healthy) and dose (8mg IV, 20mg IV and 40mg IV) and dose by population interaction. The fixed effects model will also contain a categorical effect for sex and a continuous effect for age. The present study will enroll older male and female subjects, while P001 enrolled younger male subjects. Sex and age are not expected to impact PK. An unstructured covariance matrix will be used to allow

for unequal population variances via the REPEATED and GROUP statement in SAS PROC MIXED. Kenward and Roger's method will be used to calculate the denominator degrees of freedom for the fixed population effect (DDFM=KR). Ninety-five percent (95%) CIs for the least squares means for each population by dose will be constructed on the natural log scale and will reference the t-distribution. Exponentiating the least-squares means, and their corresponding 95% CIs will yield estimates for the population geometric means and confidence intervals about the geometric means on the original scale.

Part 2:

Geometric means and 95% confidence intervals (based on a t-distribution) will be provided for AUC0-168, Cmax, and C168 obtained following the last multiple dose. Median, minimum, and maximum will be provided for Tmax.

Secondary Analysis: Comparison to Healthy Subjects

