To compare subjects with ESRD on HD to subjects with normal renal function at the same dose level, a two-sided 90% confidence interval for the true difference in means (ESRD on HD – normal renal function, at the same dose level) will be calculated for each PK parameter using the mean square error from the PK model described above and referencing a t-distribution. For each dose level of ESRD on HD, these confidence limits will be exponentiated to obtain the 90% confidence interval for the true ratio of geometric means (ESRD on HD/normal renal function, at the same dose level) for each PK parameter.

Dose Proportionality

An exploratory analysis will be conducted to preliminarily assess dose proportionality of MK-2060 AUC0- ∞ , AUC0-168hr, Cmax and C168hr in ESRD on HD participants, using the power law model. Separately for each PK parameter, individual PK values will be natural log transformed and evaluated with a linear regression model having ln(dose) as an explanatory variable. A least square estimate and 95% confidence interval for the slope associated with ln(dose) will be obtained from the model.

A plot of the observed PK data versus dose will be provided along with an estimated regression line on the raw scale and a 95% Schéffe confidence band.

Descriptive Statistics

Individual values will be listed for each PK parameter (including Tmax and apparent terminal t_{1/2}, CL, Vz) by treatment, and the following (non-model-based) descriptive statistics will be provided: N (number of subjects with non-missing data), arithmetic mean, standard deviation, arithmetic percent CV (calculated as 100 x standard deviation/arithmetic mean), median, minimum, maximum, geometric mean, and geometric percent CV (calculated as 100 x sqrt(exp(s²) - 1), where s² is the observed variance on the natural log-scale).

Pharmacodynamics

Secondary Hypothesis

Part 1:

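### Section 9.9's 90% CI half-widths for the ESRD/healthy PK ratios are unadjusted 6-versus-6 figures, while Section 9.6 plans an age- and sex-adjusted interval that is generally wider

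*Combined protocol and SAP*

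**What the plan says.** Comparing ESRD with healthy PK is a secondary estimation objective of Part 1 (Section 3): parameters "following administration of a single dose will be estimated and compared to participants with normal renal function (historical controls in PN001").

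Section 9.6 fits log-transformed PK parameters with population, dose (8, 20 and 40 mg) and their interaction, allowing a different variance in each population. "The fixed effects model will also contain a categorical effect for sex and a continuous effect for age". It then notes: "The present study will enroll older male and female subjects, while P001 enrolled younger male subjects". Section 4.2 likewise describes the comparison as "assessed by comparing data in this study to the data in young normal healthy subjects in PN001". The per-dose 90% CI for the ratio is calculated "using the mean square error from the PK model described above and referencing a t-distribution".

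Section 9.9 gives the expected precision of that ratio. It takes 6 participants per population at 20 mg and the PN001 between-subject SDs (0.199 for AUC0-168hr, 0.169 for Cmax), doubled for ESRD, and concludes that the "half width of the 90% CIs of GMRs for MK-2060 AUC0-168hr and Cmax on the log scale will be 0.329 and 0.279". It converts these to multipliers of 1.39 and 1.32. For an observed AUC0-168hr ratio of 1.50 it adds: "then the 90% CI for the GMR would be 1.08 to 2.08". It also says the sample size "was not chosen to satisfy any a priori statistical requirement". It does not mention age, sex or the three-dose model.

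**The concern.** The precision statement and the planned analysis describe different intervals. Age is strongly confounded with population, because PN001 enrolled younger men and Part 1 enrols people aged 40 to 80. Sex can be estimated only within the ESRD group, because PN001 had no women. Putting both terms in the model therefore adds variance to the population contrast at each dose. Section 9.6 does not expect age or sex to affect PK, so the plan anticipates no compensating fall in residual SD.

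Section 9.9 is the only place that says how precisely the ESRD/healthy ratio will be estimated. A reader applying its multipliers would generally expect tighter ratios than the planned model gives at the same SDs.

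**Working it through.** **1. Reproducing Section 9.9.** Inputs from 9.9: n = 6 per population, healthy SD s, ESRD SD 2s. The 90% level is from 9.6.

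Half-width = t(0.95, 10 df) × sqrt((s² + (2s)²)/6), with t = 1.812.

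- AUC0-168hr: sqrt((0.199² + 0.398²)/6) = 0.1817; × 1.812 = 0.329; exp(0.329) = 1.39.
- Cmax: sqrt((0.169² + 0.338²)/6) = 0.1543; × 1.812 = 0.280 (stated 0.279); multiplier 1.32.
- Example: 1.50/1.39 = 1.08 and 1.50 × 1.39 = 2.08.

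For AUC0-168hr, other constructions do not match: normal quantile 0.299, Welch df 0.342, no inflation 0.208, inflation in both groups 0.416, 95% level 0.405. The stated figures are the unadjusted 6-versus-6 intervals.

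**2. The three-dose model without covariates.** With 6 per cell, each population variance has 18 − 3 = 15 df. The contrast at one dose keeps SE 0.182, with Satterthwaite df = 15 × (1 + 4)²/(1 + 16) = 22.1. The half-width is 0.312 for AUC0-168hr (Cmax 0.265). Pooling over doses alone narrows the interval slightly.

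**3. Adding age and sex.** Assumptions not in the documents:

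- PN001 ages uniform over the range shown;
- ESRD ages uniform over 40-80 (the Section 5.1 limits);
- 6 healthy men at each dose (9.9 gives 6 for 20 mg only);
- 2 women among the 6 active ESRD participants at each dose.

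The model has 36 participants, six population-by-dose cells plus age and sex, group-specific variances at 9.9's SDs, and df from the expected REML information. Values are medians over simulated age sets for the 20 mg contrast in AUC0-168hr.

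| PN001 ages | SE | df | Half-width | Multiplier |
|---|---|---|---|---|
| Stated in 9.9 | 0.182 | 10 | 0.329 | 1.39 |
| 18-65 | 0.204 | 21.9 | 0.350 | 1.42 |
| 18-55 | 0.218 | 23.9 | 0.373 | 1.45 |
| 18-50 | 0.230 | 24.9 | 0.393 | 1.48 |
| 18-45 | 0.247 | 25.4 | 0.422 | 1.53 |
| 20-40 | 0.272 | 24.7 | 0.465 | 1.59 |

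Over the same age ranges, Cmax runs from 0.297 to 0.397 (multipliers 1.35 to 1.49) against 0.279. The 1.50 example becomes about 1.06-2.13 (1.50 divided and multiplied by 1.42) for ages 18-65, and 0.94-2.39 (by 1.59) for ages 20-40.

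**4. Sensitivity, AUC0-168hr, over the same age ranges.**

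- One active woman per dose: 0.338-0.459.
- No active woman: 0.329-0.445 (Cmax 0.280-0.376), so no widening at 18-65. Section 6.3.2 requires at least 2 women per panel of 8. Under random 6:2 allocation, the chance that none receives active drug at a dose is at most 1/C(8,2) = 1/28 = 3.6%.
- Share of age sets wider than 0.329 at PN001 18-65: 51% with no active woman, 79% with one, 100% with two. At 20-40 it is 100% in each case.
- 8 healthy men per dose: 0.340-0.436.
- With the Kenward-Roger covariance correction, 2 active women: 0.352-0.481.
- One pooled mean square error (28 df), 2 active women: 0.354-0.460.
- Ratio of adjusted to unadjusted half-width, 2 active women: 1.07-1.40 with no SD inflation, 1.06-1.41 at 2-fold, 1.05-1.30 at 3-fold.
- With the 40 mg PN001 GCVs in Section 4.3.4 (17.6% and 11.8%, ln SDs 0.175 and 0.118) doubled for ESRD: AUC0-168hr 0.306-0.407 against 0.289 unadjusted, Cmax 0.207-0.275 against 0.195.

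A second set of age assumptions, indexed by mean age gap and with 2 to 6 women per panel of 8, gave 0.34-0.44 for a 5-year gap, 0.37-0.46 for 15 years, 0.40-0.48 for 23 years and 0.46-0.59 for 31-33 years. Every scenario median exceeded the stated figure.

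**The case against.** The stated figures follow correctly from disclosed inputs. The sentence is conditional on 6 per population and the given SDs, and the section presents its output as expected precision, so the figures can be read as a simplified planning calculation. That is fair as to intent. But nothing in 9.9 or elsewhere says age and sex are left out, and the multipliers and worked example are presented as applying to this study's ratios.

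Uncertainty about the ESRD SD is as large as the covariate effect. Section 9.9 cites 2- to 3-fold inflation and uses 2; at 3-fold the unadjusted AUC0-168hr figure is already 0.466. With no inflation the adjusted values (0.224-0.291) all fall below 0.329. This stands: the check does not show that the observed intervals will exceed the stated ones, only that adjusted intervals are generally wider at the same SDs.

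No sample size, hypothesis or dose step depends on the half-widths. Sections 2.2.2 and 4.3.4 show that Part 1 dosing is complete and its PK has been modelled, and the reported interval will come from the 9.6 model in any case. This also stands and limits the consequence.

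Section 9.6 could be read as borrowing only the model's mean square error for a raw-mean comparison, which would give about 0.31. That reading does not fit the adjusted least-squares means that 9.6 specifies.

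**Conclusion.** The concern holds. The mismatch between 9.9 and 9.6 is certain; its size is not. At 9.9's SDs and with 2 active women per dose, the planned AUC0-168hr half-width is about 6% to 41% above the stated one (0.350/0.329 to 0.465/0.329) as the assumed PN001 age range goes from 18-65 to 20-40. It is about equal to the stated figure in the unlikely case of PN001 ages up to 65 and no active woman at that dose. The exact value needs the PN001 ages, the numbers per dose and the sex split among active participants, none of which the documents give. This is an overstated precision for a secondary estimation objective and does not affect the design or conduct of the trial.

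**What to change.** Keep the age- and sex-adjusted model as the main analysis. In Section 9.9, recompute the half-widths, multipliers and worked example for that model, using the actual PN001 ages and numbers per dose. At minimum, label the present figures as unadjusted, 6 versus 6, excluding age and sex.

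Optionally, report per-dose ratios with 90% CIs from the same model without age and sex, marked as supportive and as specified after Part 1 data were available. These would be a new fit for each of the four modelled PK parameters, and the ratios would absorb any age and sex effects.

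The required change costs one recalculation and a wording edit, or the label alone. The stated precision becomes somewhat less favourable. With Part 1 dosed, the change corrects the record only.

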4.3.2 Starting Dose for This Study

The clinical conduct of the Phase I study in healthy male participants (PN001) evaluating safety, tolerability, and PK of MK-2060 has completed. The highest single IV dose of 40 mg has been well tolerated.

In healthy participants the 8 mg IV dose was well-tolerated and lacked a significant pharmacodynamic effect (maximum observed aPTT increase was 1.4-fold compared to baseline), thus it has been selected as the starting dose for Panel A in the current trial. Selection of this dose will allow the assessment of the impact of renal impairment and HD on MK-2060 PK by direct comparison of the data from the 8 mg IV dose in normal healthy subjects in PN001. Please refer to Section 4.2 above for further discussion of why significant PK differences with MK-2060 in older adult participants with ESRD on HD is not anticipated.

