9.3 Hypotheses/Estimation

Secondary

1. **Hypothesis (Part 1):** The true fold increase in aPTT 168 hours after a single well-tolerated dose of MK-2060 in older subjects with ESRD on HD is at least 1.5.
2. **Hypothesis (Part 2):** The true fold increase in aPTT 168 hours after the last dose following an IV loading dose and three maintenance doses of MK-20160 in older adult participants with ESRD on HD at least 1.5.

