Individual aPTT fold-change from baseline values will be natural log-transformed and evaluated with a linear mixed effects model containing fixed effects for treatment and time and treatment by time interaction and random effect for participant. Least squares means and 95% confidence intervals for each treatment, and for the between-treatment differences (MK-2060 – placebo) and 90% CI at each dose level, will be obtained by time. These estimates will be back-transformed to obtain GM aPTT fold-change from baseline by treatment and time and the GMR (MK-2060 fold-change from baseline/placebo fold-change from baseline) by dose and time.

The posterior probability that the true fold-increase from baseline in aPTT 168 hours after a single dose is at least 1.5 will be calculated for each dose assuming normality and using a non-informative (Jeffrey's) prior. A 60% posterior probability for at least one dose level that also exhibits an acceptable safety profile will satisfy the secondary pharmacodynamics hypothesis. In addition, the proportion of subjects with a fold-increase in aPTT 168 hours after a single dose of at least 1.5 will be tabulated.

FXI activity levels, FGA and PT will be evaluated in a similar fashion. Additional model-based analysis may be employed to further explore PD endpoints over time.

Descriptive statistics will be provided for PD endpoints by treatment and time.

Part 2:

As in Part 1, individual aPTT fold-change from baseline values will be natural log-transformed and evaluated with a linear mixed effects model incorporating the longitudinal effects of measurements at the three weekly time points. An unstructured covariance matrix will be used to model the correlation between different measurements within the same subjects. Kenward and Roger's method will be used to calculate the denominator degrees of freedom for the fixed effects. Least squares mean and 95% confidence intervals for each treatment, and for the between-treatment differences (MK-2060 – placebo) and 90% CI will be obtained. These estimates will be back-transformed to obtain GM aPTT fold-change from baseline by treatment and time and the GMR (MK-2060 fold-change from baseline/placebo fold-change from baseline) by time.

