The posterior probability that the true fold-increase from baseline in aPTT is at least 1.5 will be calculated at each of the three weekly time points assuming normality and using a non-informative prior. A 60% posterior probability for at least one of the three time points that also exhibits an acceptable safety profile will satisfy the secondary pharmacodynamics hypothesis. In addition, the proportion of subjects with at least 1.5 fold increase in aPTT 168 hours after the last dose will be tabulated.

FXI activity levels, FGA and PT will be evaluated in a similar fashion. Additional model-based analysis may be employed to further explore PD endpoints over time.

Descriptive statistics will be provided for PD endpoints by treatment and time.

PK-PD

The relationship between plasma concentrations and aPTT, FXI activity, FGA, and PT will be explored graphically. Upon visual inspection, additional model-based analysis may be employed to further explore the PK/PD relationship.

General

For all analyses, data will be examined for departures from the assumptions of the statistical model(s) as appropriate; e.g., heteroscedasticity, nonnormality of the error terms.

Distribution-free methods may be used if a serious departure from the assumptions of the models(s) is observed, or suitable data transformations may be applied.

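### Section 9.9 quotes 72.3% and 84% without the true fold increase they assume; at the only value it names (1.5), one dose or time point meets the 60% criterion 40% of the time, and the any-of-three success rules are not evaluated

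*Combined protocol and SAP*

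**What the plan says.** Section 9.9 (Pharmacodynamics) gives two operating characteristics, both at a true CV of 30%. For Part 1, with 6 active and 2 placebo per dose, "there is approximately 72.3% probability of yielding at least 60% posterior probability that the true fold increase is at least 1.5". For Part 2, with 15 active and 5 placebo, "there is approximately 84% probability of yielding at least 60% posterior probability that the true fold increase is at least 1.5". In both parts the assumed effect is that the fold increase 168 hours after a "single well-tolerated subcutaneous dose relative to placebo is at least 1.5". No other value of the true fold is given.

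Section 9.6 defines the Part 1 criterion on a different quantity: "The posterior probability that the true fold-increase from baseline in aPTT 168 hours after a single dose is at least 1.5", assuming normality with a non-informative prior. The secondary hypothesis is then satisfied as follows:

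- **Part 1:** "A 60% posterior probability for at least one dose level that also exhibits an acceptable safety profile".
- **Part 2:** "A 60% posterior probability for at least one of the three time points that also exhibits an acceptable safety profile".

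The Part 2 hypothesis in Section 9.3 concerns one time only, "168 hours after the last dose following an IV loading dose and three maintenance doses". Section 9.8 makes no multiplicity adjustment.

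**The concern.** The assumed effect is a range whose lower end is the threshold itself. Read literally, 72.3% and 84% should hold from 1.5 upward, so they should hold at 1.5. A posterior-probability rule with a 60% cut-off cannot behave that way at its own boundary, so the figures must come from a larger effect that is not written down.

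Two further mismatches make the figures hard to use. The comparator, route and number of doses in 9.9 differ from those in 9.3 and 9.6. The figures also take no account of there being three chances to succeed in each part.

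These are the only operating characteristics given for the trial's only formal hypotheses. A reader cannot tell which true effect they describe, or how often success would be declared when the true fold is below 1.5.

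**Working it through.** **Inputs.** CV 30%, 6+2 per dose and 15+5 (Section 9.9); threshold 1.5, 60% posterior probability, normality on the log scale, non-informative prior, any-of-three rules (Section 9.6); three dose levels (Section 4.1).

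**Formula.** Log-scale SD = √ln(1 + 0.3²) = 0.2936. With the usual reference prior, a posterior probability of at least 60% is equivalent to

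t = [mean ln(fold) − ln 1.5] / SE ≥ t(0.60, df).

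The probability of meeting it is the upper tail of a non-central t with non-centrality ln(true fold / 1.5) / SE.

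| Set-up | SE | df | t(0.60, df) |
|---|---|---|---|
| From baseline, n=6 | 0.2936/√6 = 0.1198 | 5 | 0.267 |
| From baseline, n=15 | 0.2936/√15 = 0.0758 | 14 | 0.258 |
| Versus placebo, 6 v 2 | 0.2936·√(1/6+1/2) = 0.2397 | 6 | 0.265 |
| Versus placebo, 15 v 5 | 0.2936·√(1/15+1/5) = 0.1516 | 18 | 0.257 |

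**Step 1: try to reproduce the plan's figures at 1.5.** The non-centrality is zero, so the probability is 1 − 0.60 = 40.0% in all four set-ups. The alternative Jeffreys-rule degrees of freedom give 40.3% to 41.4%. Neither 72.3% nor 84% is reproduced.

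**Step 2: find the fold that returns them.**

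| Stated figure | From baseline | Versus placebo |
|---|---|---|
| 72.3% (Part 1) | 1.66 | 1.84 |
| 84% (Part 2) | 1.65 | 1.81 |

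**Step 3: probability for one dose or time point.**

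| True fold | n=6 | n=15 | 6 v 2 | 15 v 5 |
|---|---|---|---|---|
| 1.4 | 20.4% | 12.2% | 29.4% | 23.9% |
| 1.5 | 40.0% | 40.0% | 40.0% | 40.0% |
| 1.65 | 70.5% | 84.2% | 55.7% | 64.6% |
| 2.0 | 98.4% | >99.9% | 82.7% | 95.0% |

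**Step 4: any-of-three, Part 1** (from baseline, n=6, independent panels).

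- All doses at 1.5: 1 − 0.6³ = 78.4%.
- All at 1.4: 1 − (1 − 0.2041)³ = 49.6%.
- An assumed gradient of 1.1/1.3/1.5: 1 − 0.9977 × 0.9256 × 0.6 = 44.6%.
- One dose at 1.5 and two at 1.0: 40.0%.

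**Step 5: any-of-three, Part 2** (from baseline, n=15, simulated with three equally correlated time points). The documents give no within-subject correlation, so a range is shown.

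| All folds at | Correlation 0 | 0.5 | 0.9 |
|---|---|---|---|
| 1.4 | 32% | 26% | 18% |
| 1.5 | 78% | 65% | 51% |
| 1.6 | 98% | 91% | 81% |

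The any-of-three rule does not explain the stated figures either. The Part 1 figure is expressly per dose, and at 1.5 the three-dose value is 78.4%, not 72.3%. In Part 2, 78.4% is the ceiling at 1.5 for non-negatively correlated time points, so 84% cannot arise there.

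**The case against.** The strongest reply is that nothing has been miscalculated. One common fold gives both figures to within about 2 percentage points: 1.65 from baseline gives 70.5% and 84.2%, and 1.82 to 1.83 against placebo gives about 71–72% and 85%. On this view 9.9 omits an input and is loosely worded. That is correct about the sums. However, the text as written still attaches 72.3% and 84% to a condition whose lower end yields 40%.

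Replacement figures also depend on the comparator. On 9.9's placebo-relative wording, a fold of 1.65 gives 55.7% and 64.6%. If Part 1 placebo were pooled over panels, any-of-three against placebo would be 65% at 1.5 and 47% at 1.4. This stands as a reason to settle the comparator first. Section 9.6 defines the posterior on change from baseline, so those figures are the natural default.

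Equal folds at all three Part 1 doses are not the expected case. At 8 mg in healthy participants the "maximum observed aPTT increase was 1.4-fold compared to baseline" (Section 4.3.2), and Section 4.3.3 predicts about 2-fold at 168 hours for 40 mg. At 2.0 that dose alone passes 98.4% of the time from baseline. This also stands, and the equal-fold results should be read as illustrations.

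Finally, the practical effect is small. The hypothesis is secondary, the sample size rests on the primary objectives, all 24 Part 1 participants had been dosed by 09-Oct-2020 (Section 2.2.2), and Section 4.3.4 projects more than 90% of Part 2 participants at 1.5-fold at trough. This limits the severity but leaves the stated probabilities uninterpretable.

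**Conclusion.** The concern holds. At the only effect Section 9.9 names, the per-comparison probability is 40%, against a stated 72.3% and 84%. Those figures correspond to unstated folds of about 1.65 from baseline or a little over 1.8 against placebo. The 40% needs only normality and the usual non-informative prior. The other values also assume a CV of 30% and a variance estimated from the participants in that comparison; the Part 2 any-of-three values further assume a correlation between 0 and 0.9.

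Section 9.9 also describes a different comparator, route and dosing from 9.3 and 9.6, and leaves the any-of-three rules unevaluated. With all folds at 1.4 those rules succeed about 50% of the time in Part 1 and 18–32% in Part 2. This should be fixed, but it does not threaten the primary objectives or the sample size.

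**What to change.** Restate the pharmacodynamic part of Section 9.9 as follows.

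1. Write down the assumed true fold(s) and define them from baseline, as in 9.3 and 9.6. If the placebo-corrected ratio is intended, reconcile 9.3 and 9.6 with 9.9 first and quote the 6 v 2 and 15 v 5 figures.
2. Give per-dose or per-time-point probabilities, labelled as such. From baseline these are 40% at 1.5, about 70% (n=6) and 84% (n=15) at 1.65, and about 98% and over 99% at 2.0.
3. Give probabilities under the any-of-three rules for stated folds at each dose or time point and, in Part 2, a stated within-subject correlation. Include at least one case below 1.5 and, for Part 1, a dose gradient. Examples are about 78% (Part 1) and 51–78% (Part 2) with all at 1.5, and about 50% and 18–32% with all at 1.4.
4. Reconcile the single-time hypothesis for Part 2 in 9.3 with the three-time-point rule in 9.6, and the single subcutaneous dose in 9.9 with the IV and multiple-dose descriptions elsewhere.

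The cost is SAP wording. The quoted probabilities look less favourable at the boundary and the chance of success below 1.5 becomes visible. No extra participants are needed, and items 1 to 3 leave the analysis unchanged if the from-baseline definition is kept.
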